Sample size was calculated based on FMA-UE data obtained from our pilot study (see Preliminary Studies) to determine whether there is a statistical difference in people receiving targeted rehabilitation vs. a comparison non-targeted intervention in the present parallel arm design with 6 treatment groups. Specifically, we will test $H_0: \mu_{\text{targeted}} = \mu_{\text{non-targeted}}$, versus the two tailed alternative $H_a: \mu_{\text{targeted}} \neq \mu_{\text{non-targeted}}$. The pilot study demonstrated that the targeted (trunk restraint) group exhibited a post-training Rasch-derived FMA-UE person ability measure of 2.30 (± 1.00) logits, while the non-targeted intervention (mCIMT) group exhibited a post-training Rasch FMA-UE score of 1.42 (± 0.45) logits which yields a Cohen's d effect size of 1.13. With an alpha level = 0.05, for a two-tailed hypothesis test at a 90% power level, the sample size calculation specified that 18 individuals are needed in each group to answer the research hypothesis confidently. With 6 treatment groups,

Group data (not presented) suggested that participants demonstrated expected UE movement patterns prior to the intervention in that while attempting to reach forward they had difficulty extending the elbow while flexing the shoulder. Participants who underwent an intervention specifically aimed at altering this movement pattern demonstrated a statistically significant Pre to Post gain in voluntary elbow extension ranges of motion whereas those who underwent an intervention that was not aimed at altering the compensatory movement pattern showed very little gain in voluntary elbow extension. For example 4 out of 5 participants in the targeted treatment group showed increased elbow extension angular excursion, while 4 out

N=108. Based on the stroke rehabilitation literature we anticipate a 20% drop out rate and therefore will enroll **N=130** subjects.

Project Timeline:

	Jan	Feb	Mar	Apr	May	Jun	Jul	Aug	Sept	Oct	Nov	Dec
Yr1					Preparation and Recruitment					Enroll 20 patients		
Yr2								Enroll 48 patients				
Yr3								Enroll 40 patients				
Yr4				Complete follow-up tests					Data analysis and manuscript preparation			

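### The 20% dropout allowance was added to 108 instead of divided out, so 130 enrolled leaves about 104 completers and not 108; separately, the Project Timeline's yearly enrolment sums to 108 and not 130

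*Protocol*

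**What the plan says.** The sample size paragraph of the protocol (section D, Research Design and Methods, Study Design) takes the pilot's post-training results: a "post-training Rasch-derived FMA-UE person ability measure of 2.30 (± 1.00) logits" in the targeted arm and a "post-training Rasch FMA-UE score of 1.42 (± 0.45) logits" in the non-targeted arm, "which yields a Cohen's d effect size of 1.13". "With an alpha level = 0.05, for a two-tailed hypothesis test at a 90% power level", it concludes that "18 individuals are needed in each group to answer the research hypothesis confidently". Six groups (three severity levels by two treatments) give 108. It then states "we anticipate a 20% drop out rate and therefore will enroll" a total of 130.

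The total of 130 also appears in section A (Aim 1), in the opening of Study Design, under Recruitment, and in the human subjects section, including its planned enrolment table.

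The Project Timeline, directly after the sample size paragraph, shows 20 patients enrolled in Year 1, 48 in Year 2 and, in Year 3, "Enroll 40 patients". Year 4 contains only follow-up tests, data analysis and manuscript preparation.

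The SAP (Missing Data) keeps patients who drop out in an intention-to-treat analysis, assumes data missing at random, and uses multiple imputation.

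**The concern.** A dropout rate is a fraction of the patients enrolled. To have 108 left after losing 20%, one divides 108 by 0.80. Adding 20% to 108 gives a smaller number, and the protocol's 130 looks like the result of doing so. If so, the stated enrolment and the stated dropout rate together do not produce the stated 18 per group.

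The timeline raises a second, separate question. Its three yearly figures appear to sum to the number needed before any dropout allowance. Whoever runs recruitment would then have a schedule and a target that differ.

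At stake are the accuracy of the stated sample size justification and, if the schedule rather than the target were followed, a real loss of completers.

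**Working it through.** **Inputs** (all from the protocol's sample size paragraph and Project Timeline): means 2.30 and 1.42 logits; SDs 1.00 and 0.45; d = 1.13; two-sided alpha 0.05; power 90%; 18 per group; 6 groups; dropout 20%; enrolment 130; yearly enrolment 20, 48 and 40.

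**1. Reproduce the base figures.**
- Pooled SD = √((1.00² + 0.45²)/2) = 0.775, so d = (2.30 − 1.42)/0.775 = 1.135. The protocol gives 1.13.
- Two-sample t-test power from the noncentral t distribution, with 2n − 2 degrees of freedom and noncentrality d√(n/2): at d = 1.13, power is 0.891 for n = 17 and 0.909 for n = 18. The smallest whole number reaching 90% is 18, as stated.
- 6 × 18 = 108, as stated.

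**2. Reproduce the 130.**
- Adding 20%: 108 × 1.20 = 129.6, rounded up to 130. This matches.
- Dividing out 20%: 108/0.80 = 135. This does not match. (Rounding up within each group gives 18/0.80 = 22.5, so 23 × 6 = 138.)

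**3. What 130 delivers.**
- 130 × 0.80 = 104 completers, 4 fewer than 108; 104/6 = 17.3 per group.
- Highest dropout that leaves 108: 1 − 108/130 = 16.9%.

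**4. Sum the timeline.**
- 20 + 48 + 40 = 108, which is 22 below 130.
- If that schedule were actually followed with 20% dropout: 108 × 0.80 = 86.4, about 86 completers, or 14.4 per group.

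**5. Power on the protocol's sizing basis** (one targeted versus non-targeted comparison within a severity level, two-sided alpha 0.05, equal groups, completers only):

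| Case | n per group | Power at d = 1.13 |
|---|---|---|
| As stated | 18 | 0.909 |
| 130 enrolled, 20% dropout | 17.3 | 0.897 |
| The same, whole number | 17 | 0.891 |
| Conditional: 108 enrolled, 20% dropout | 14.4 | 0.832 |

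With the unrounded d = 1.135, power is 0.911 at 18 per group and 0.900 at 17.3.

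**The case against.** The strongest reply is that the slip costs almost nothing. Before rounding up, 90% power needs 17.3 per group at d = 1.135 or 17.5 at d = 1.13, so rounding to 18 already absorbs nearly all of the 4-patient gap. That stands. A reader might infer that the trial materially misses its 90% power; the figures do not show that. What is missed is the stated count of 18 per group.

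Second, the timeline is a planning chart. A reader might infer that recruitment would close at 108 and that power is therefore about 0.83. The documents do not support this: every other statement of the total is 130, and nothing makes the chart a ceiling or a stopping rule. It could be a remnant from before the allowance was added, or could be counting evaluable patients. Against the last reading, its labels speak of enrolling. The inconsistency stands; the 0.83 is conditional on the schedule overriding the target.

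Third, counting completers only overstates the loss, because the SAP keeps dropouts in the analysis through multiple imputation and a dropout may have contributed earlier measurements. This softens the loss but does not restore outcomes that were never observed.

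Fourth, the powers above follow the sizing paragraph and match neither planned Aim 1 analysis. The protocol's Aim 1 data analysis tests the three severity levels at 0.02, where power at d = 1.13 is about 0.82 with 18 per group and 0.81 with 17.3. The SAP tests a treatment main effect across levels at 0.05, where a simple two-sample approximation gives power above 0.99 even with 43 per arm (86/2). So the figures measure the departure from the protocol's own sizing claim and are not the trial's overall power.

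Fifth, 17.3 assumes six equal groups, and no quotas by severity level are stated. Imbalance between levels could exceed the 0.7-patient difference.

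Finally, no replacement rule appears in the readable text, but the study flow figure is not available here, so it would go too far to say that a shortfall could not be made up.

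**Conclusion.** The point holds in two limited parts.

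The dropout allowance is miscalculated: the protocol's own 20% and 130 give about 104 completers and not 108. The shortfall of 4 lowers power from about 0.91 to about 0.90 on the protocol's sizing basis, or to 0.89 at a whole 17 per group. This is an error in a key stated figure with a small consequence.

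The Project Timeline is inconsistent with the enrolment target by 22 patients. The target of 130 is otherwise unambiguous, so this is a scheduling error. It would matter (about 86 completers, power about 0.83) only if recruitment were actually run to the schedule.

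The sizes rest on 20% dropout, equal groups, d = 1.13, two-sided alpha 0.05 and completers as the basis for power. The arithmetic on 130, 135, 104 and 108 needs only the stated dropout rate and counts.

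**What to change.** Keep 130 and restate what it provides, in either of two ways:
- at 20% dropout, about 104 expected completers, about 17 per group, with power of about 89–90% on the stated sizing assumptions; or
- 18 completers per group, provided that dropout does not exceed about 17%.

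Correct the Project Timeline so that the yearly enrolment sums to 130.

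This is a change to protocol wording only. It adds no patients beyond those already planned and alters neither design nor analysis. The cost is a slightly less favourable statement of power or of tolerated dropout. If the sponsor would rather expect 108 completers at 20% dropout, the total becomes 135 (138 if each group is rounded up separately), which means 5 to 8 more patients.

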One purpose of the present proposal is to explore the neuromechanical mechanisms contributing to post-stroke UE recovery. There is evidence supporting the hypothesis that several neuromechanical (i.e., kinematic and electromyographic (EMG)) factors are key to recovery. Individuals with stroke demonstrate reduced voluntary elbow extension range of motion⁵² which may be at least partially explained by abnormal elbow muscle co-activity between biceps and triceps.⁵³ Together, these impairments contribute to reduced ability make smooth reaching movements throughout the workspace.⁵⁴ Given this limitation, people with stroke recruit the trunk as an extra degree of freedom.⁵⁴ Anterior trunk flexion is used in place of elbow extension for reaching movements. UE motor recovery is characterized by improved elbow extension,⁵⁵ reduced anterior trunk motion,⁵⁶ and reduced muscle co-activity.⁵⁷

Here we aim to investigate the influence of neuromechanical mechanisms contributing to the treatment related changes in participants' Rasch FMA-UE person ability measure. By investigating the relationship of neuromechanical factors to a person's FMA-UE measure, we will learn more about what neuromechanical factors or mechanisms underlie a person's location within this classification system. As noted in the brief literature review above, several studies relate neuromechanical factors to UE recovery. But in these studies, UE recovery is defined in terms of performance of a single task (e.g., reach-to-point) or in terms of a patient's aggregate score on an assessment. Here, our measurement framework enables us to investigate how neuromechanical factors influence re-acquisition of the underlying construct "UE motor ability" which is defined in terms of specific FMA-UE items that a patient could/could not perform prior to rehabilitation but gained the ability to perform after rehabilitation.

2g. The time-course of UE recovery

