We have previously published our standardized procedures for neuromechanical evaluation.³² Subjects will be seated on a backless stool with the start posture standardized. Using their affected UE, subjects will perform 10 trials of reach-to-grasp (or touch) a soda can which will be placed at a location equal to 80% of arm’s length at midline, a location affording maximum shoulder flexion and elbow extension.⁵⁴ *No trunk constraint or arm support will occur during testing.* Kinematic data will be recorded with a 10-camera motion analysis system (PhaseSpace Inc) at a sampling frequency of 480 Hz using a marker set defined in our previous work.³² Kinematic data will be filtered with a 4th-order Butterworth low-pass filter (cutoff frequency of 12 Hz) then processed through a Visual 3D kinematic model using custom Matlab functions. Surface EMG electrodes will be applied to the center of the muscle bellies of the biceps (BI) and triceps (TRI) according to SENIAM procedures. The muscles are chosen because of their important roles as agonist (TRI) and antagonist (BI) for forward reach. Baseline EMG (16-channel wireless system, Motion Lab Systems) values will be collected (2000 Hz) with the limb at rest in order to identify the ambient noise and isoelectric muscle activity signal level, then collected during reach-to-grasp movement. EMG data will be bandpass filtered (5 Hz – 1 kHz), demeaned, rectified and low-pass filtered with a fourth-order, zero-lag digital Butterworth filter (cutoff 20 Hz).

We will use Transcranial Magnetic Stimulation (TMS) to measure Neural Excitability: TMS analysis will be conducted at five time points (pre-intervention, end of weeks 1,2, and 3, and post-intervention)

Transcranial Magnetic Stimulation (TMS) is a means measuring the excitability of brain activity by generating a magnetic field that induces an electrical impulse into specific regions of the brain. The handheld TMS device that will be used in this study are two coils positioned side by side in a figure eight fashion. These coils, encased in plastic housing, produce a magnetic field that is only able to penetrate the outer layers of the cortex of the brain without causing pain or discomfort to the patient⁶⁹.

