Rationale: Very little is known about the neural and biomechanical mechanisms contributing to post-stroke UE motor impairment. Identification of the critical kinematic and neural aspects of reach contributing to changes in UE motor impairment occurring with therapy will permit refinement of existing and development of new interventions specifically targeted at improving these motor control process.

Approach: As described in the procedures above, we will collect kinematic and electromyographic (EMG) data to provide information about motor control strategies (kinematic) neural influences on motor output (EMG) responding to therapy.

Dependent Variable: The dependent variable will be change in UE motor impairment as measured by the percent change in the Rasch FMA-UE occurring from pre- to post-intervention as calculated above.

Independent Variables: We hypothesize that 3 independent variables will explain changes in UE motor impairment expected to occur with rehabilitation. These variables will be measured as the percent change in each variable occurring from pre- to post-intervention (post minus pre divided by pre). The variables were chosen because they are reasonable measures of "normal" movement based on the literature, motor control theory and clinical interpretation. Two kinematic variables (trunk movements, elbow extension range of motion) provide information about the strategy utilized to execute the movement. Trunk movement will be calculated as the cumulative distance a marker placed at T-10 travels during the reach. Voluntary elbow extension is calculated as difference between elbow joint angle at start and the joint angle at touch. One EMG variables (Biceps-Triceps co-

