We will first investigate assumptions of normality for all variables via visual inspection of probability plots and statistically verified with the Kolmogorov-Smirnov f test. If the data are not normally distributed, they will be logarithmically transformed. Although we expect that all variables will be associated with the FMA-UE person-measure, we do not expect that a simple linear trend will best describe this relationship. It is likely that the response variables have a different impact on the FMA-UE person-measure according the level of UE motor impairment. Thus it is likely that a polynomial relationship exists between the response variables and the dependent variable. To determine whether a linear or polynomial regression model best fits our data we will first cross-plot each response variable against the dependent variable. Visual inspection of the scatterplot will help to facilitate the appropriate model and identify outliers which may affect the model. Outlier data points beyond 3 standard deviations of the mean value of that variable will be inspected to determine if the data was entered correctly. If not, the data point will be considered an aberrant rating and dropped from analysis. When it is determined that a quadratic trend likely best fits the data, we will transform the variable to its quadratic term via its unstandardized residual to compensate for multicollinearity. We will then apply a general linear model regression procedure to the data using SAS. A forced-entry procedure will be employed in which all variables will be examined for each model. Adjusted R-square values, p-values and 95 percent confidence intervals will be calculated.

We will test significance of the coefficient of determination (adjusted R-square value) for each response variable. The null hypothesis tested is that there is no significant association between each response variable and the dependent variable, meaning that the response variable does not contribute to UE motor ability (FMA-UE person measure). The alternative hypothesis is that the association is significant meaning that the response variable is associated with UE motor ability (FMA-UE person measure). We will reject the null hypothesis if $p < 0.05$ which will lead to the conclusion that the response variable does not contribute to the FMA-UE score at a 0.05 significance level.

Specific to Aim 3: Determine critical predictors of the time-course of response to targeted rehabilitation.

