Data analysis: Data from participants in targeted-rehabilitation protocols will be pooled and analyzed. Three models will be tested in accordance with our a-priori hypothesis that each level of impairment (mild, moderate, severe) should show distinct patterns of recovery, i.e., we expect 3 classes of recovery. Specifically, we will test whether there is one overall pattern of recovery that describes the entire sample (1-class), whether there are two patterns of recovery within the sample (2-class) or whether there are three patterns of recovery in the sample (3-class). The models are not nested (a 1-class model is not a subset of the 2-class model) because different individuals make up each class. Therefore the chi-square model comparison test is not appropriate. Instead, we will define the best fitting model as the one having the lowest Bayesian Information Criteria (BIC) and an entropy value closest to 1.0.

To determine the best predictors of recovery patterns we will use logistic regression to relate recovery pattern (growth class membership) to kinematic and EMG variables hypothesized to be important predictors of recovery. The predictors hypothesized to be important are baseline elbow extension AROM, amount of trunk movement, and muscle co-activity. The predictor variables entered into analysis will be collected pre-intervention. Predictors will be examined to determine those which significantly discriminate class membership. Because the predictors are allowed to vary across classes, the analysis will provide a means of examining whether predictors of one trajectory differ across each trajectory. For example, loss of elbow extension AROM may be the most significant predictor of membership in one class, while inability to activate agonist muscles may be the most significant predictor of another recovery pattern.

Methods specific to the SUBSTUDY

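### Aim 2 tests elbow extension and trunk movement one at a time in a shared model, with no check on their overlap, so it can miss a contribution that the pair makes jointly

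*Protocol*

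**What the plan says.** Protocol section D, Procedure for Neuromechanical Evaluation, standardizes the start posture and has subjects "perform 10 trials of reach-to-grasp (or touch) a soda can which will be placed at a location equal to 80% of" arm's length. It adds: "No trunk constraint or arm support will occur during testing". Section B, 2f, describes the substitution: "Anterior trunk flexion is used in place of elbow extension for reaching movements". It also characterizes recovery as more elbow extension and less trunk motion.

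Section D, Specific to Aim 2, enters three predictors, each as a percent change from pre to post. For the elbow: "Voluntary elbow extension is calculated as difference between elbow joint angle at start and the joint angle at touch". For the trunk: "Trunk movement will be calculated as the cumulative distance a marker placed at T-10 travels during the reach". The third is a biceps-triceps co-contraction index. There is one regression per treatment, pooled over impairment levels, and "A forced-entry procedure will be employed in which all variables will be examined for each model". A coefficient of determination is then tested for each variable at p<0.05. Multicollinearity is mentioned once, for a variable and its own quadratic term. The same text attaches the conclusion of no contribution to rejecting the null hypothesis, which is the wrong way round.

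Specific to Aim 3 relates growth class to the baseline values of the same measures by logistic regression: "Predictors will be examined to determine those which significantly discriminate class membership". It gives no entry method and no alpha. The SAP covers Aim 1 only.

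**The concern.** With a fixed target and a free trunk, a patient who leans further needs less elbow extension to reach the can. In a model holding both variables, each coefficient asks what one adds with the other held constant. If the two overlap strongly, neither may pass its own test even when reach strategy as a whole is clearly related to outcome, or one may be picked largely by chance. Aim 2 exists to name the critical neuromechanical factors and to guide refinement of treatments, so a false statement that a factor does not contribute would misdirect that work.

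**Working it through.** **Sample size per model (Protocol, Study Design).** The plan's own figure reproduces. Pooled SD = √[(1.00² + 0.45²)/2] = 0.775; d = (2.30 − 1.42)/0.775 = 1.13; a two-sided t-test at 0.05 with 90% power needs 17.5, so 18 per group. Then 18 × 6 = 108, or 54 per regression. With 130 enrolled and 20% dropout, 130 × 0.80 = 104, or 52 per regression. No power or predictor correlation is stated for Aims 2 or 3.

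**How tight the tie could be (assumed geometry).** Take a planar arm with two equal links of 0.5 arm lengths and a shoulder-to-can distance D. The elbow angle at touch satisfies cos θ = (0.25 + 0.25 − D²)/0.5.
- D = 0.8 (no forward shoulder shift): cos θ = −0.28, θ = 106°.
- D = 0.7 (shift of 10%): cos θ = 0.02, θ = 89°.
- D = 0.6 (shift of 20%): cos θ = 0.28, θ = 74°.

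That is the ideal case. A simulation on this geometry (start angle 45 to 60 degrees; baseline elbow extension above 5 degrees for percent change) gives r = −1.0 at baseline but only about −0.57 to −0.66 for percent changes, with no other movement. Adding movement of other segments, start-angle variation, excess path length and failure to reach the can gives about −0.9 to −0.4 at baseline and about −0.5 to −0.15 for percent changes.

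**Consequence in Aim 2.** The simulated regressions have three predictors. Effects run in the protocol's expected direction (more elbow extension and less trunk movement go with a better outcome), and the EMG index has no effect. Each variable's t-test at 0.05 is compared with the joint test F = [(RSS without the pair − RSS full)/2] / [RSS full/(n − 4)]. R² for the pair and |r| are assumptions. VIF = 1/(1 − r²). Entries are the percentage of trials in which the pair is jointly significant and neither variable is (n = 52, 8,000 runs per cell).

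| | r = 0 | 0.3 | 0.5 | 0.7 | 0.8 | 0.9 |
|---|---|---|---|---|---|---|
| VIF | 1.0 | 1.1 | 1.3 | 2.0 | 2.8 | 5.3 |
| Equal effects, R² 0.15 | 2 | 9 | 19 | 34 | 44 | 55 |
| Equal effects, R² 0.25 | 1 | 5 | 12 | 31 | 46 | 66 |
| One variable only, R² 0.15 | 1 | 3 | 7 | 20 | 31 | 47 |
| One variable only, R² 0.25 | 0 | 1 | 4 | 14 | 27 | 50 |

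The joint test has about 72% power at R² 0.15 and 94% at 0.25, whatever r is.

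With n = 54 and equal effects, the rates at |r| 0.2, 0.4 and 0.6 are 4, 11 and 25% for R² 0.20, and 1, 4 and 12% for R² 0.30. At R² 0.15 and |r| 0.15 to 0.65 the range is 5 to 30%.

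**Consequence in Aim 3, if both variables enter one model.** Assume two balanced classes, n = 52, three predictors and a linear-predictor SD of 1.1. The 2-df likelihood-ratio test has about 89% power. The pair is significant with neither variable significant in 2% of trials at r = 0, then 16, 32, 54 and 69% at −0.4, −0.6, −0.8 and −0.9. At SD 0.9 the last four are 18, 32, 48 and 57%; at SD 1.4 they are 9, 21, 52 and 69%.

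**The case against.** A reader might infer that the two variables are almost one quantity measured twice, so that Aim 2 will usually miss both. The documents do not support that.
- The trunk measure is the path length of a T-10 marker, not forward displacement of the shoulder. Trunk rotation, scapular motion, grasping versus touching, and falling short of the can all loosen the tie.
- Aim 2 analyses percent changes, which weakens the correlation further.
- Counting every trial in which neither variable is significant would mix ordinary low power with overlap. At R² 0.15 and n = 52 that happens in 23% of trials with no correlation at all.

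The test itself is also unclear. If the per-variable coefficient of determination comes from one-variable models, overlap hides nothing. Forced entry of all variables points the other way, but the text does not settle it. Scatterplots and an overall adjusted R-square are planned and might reveal a joint contribution. However, the decision rule does not use them, and the overall R-square includes the EMG index.

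A reader might also take forced entry and p<0.05 to apply in Aim 3. They are stated for Aim 2 only.

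These points limit the size of the problem. They do not supply the missing overlap check or joint test.

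**Conclusion.** The point holds as a gap in pre-specification. Overlap between elbow extension and trunk movement is likely but unquantified, and the plan has no means to detect or handle it.

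For Aim 2, at |r| 0.2 to 0.6 and pair R² 0.15 to 0.30, a joint contribution is missed by both separate tests in about 1 to 30% of trials with equal effects, and less often if only one variable has an effect. At |r| 0.8 to 0.9 the rate is about 40 to 66% with equal effects and about 20 to 50% with one. Such high correlations lie beyond what the assumed geometry gives for percent changes.

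Aim 3 is more exposed, because baseline values could plausibly reach |r| 0.4 to 0.9. This depends on both variables sharing one model, and the logistic figures assume two equal classes.

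Every rate rests on assumed correlations and effect sizes. The Aim 1 treatment comparison is unaffected.

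**What to change.** In Specific to Aim 2, Data analysis:
- State which per-variable test is meant (the coefficient in the joint model, or a one-variable R-square), and correct the reversed conclusion.
- Report the elbow-trunk correlation and the VIF.
- Test the two variables first as a block with a 2-df F test, and base any statement that reach strategy contributes on that block.
- Show each variable also in a model without the other.
- Do not conclude that one variable does not contribute from its joint-model p-value alone.

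In Specific to Aim 3, state the entry method and alpha, and use the same steps with a likelihood-ratio test. It has 2 df for two classes; for three classes in one multinomial model it has 2 × (3 − 1) = 4 df.

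The cost is a paragraph of text and one extra test per model, with no new data. The downside is a weaker claim about elbow versus trunk separately when the two overlap strongly. If the correlation proves small, the separate tests stand.
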